4.4.1.3.3 Duration

Duration will be computed using the same methodology as for unsolicited non-serious AEs described in [Section 4.4.1.2.5](#).

4.4.1.4 Medically-Attended Adverse Events

MAAEs that occur from Visit 1 (D0) to Visit 2 (D30[+14days]) will be recorded as unsolicited AEs on the diary card as part of all unsolicited AEs collected. Unsolicited AEs that have action taken categories 2 (health care provider contact) or 3 (Health care contact + Medication) will be summarized and presented as MAAEs between D0 visit and D30 visit.

MAAEs that occur from Visit 2 (D30 [+14 days]) to D180 (+14 days) will be recorded as such in the memory aid. An MAAE that occurs within the study period but meets the definition of an SAE should be reported only on the SAE Reporting Form, but not on the MAAE page of the CRF. Calculation methods are the same as unsolicited non-serious AEs as described in [Section 4.4.1.2](#).

4.4.1.5 Other Safety Endpoints

4.4.1.5.1 Action Taken

This information will be summarized as collected, including missing observations. No derivation or imputation will be done.

4.4.1.5.2 Seriousness

This information will be summarized as collected. No derivation or imputation will be done.

4.4.1.5.3 Outcome

This information will be summarized as collected. No derivation or imputation will be done.

4.4.1.5.4 Causality

This information will be summarized as collected. Missing causality (relationship) will be handled as described in [Section 5.3.1.2](#).

4.4.1.5.5 AEs Leading to Study Discontinuation

A flag is available in the clinical database for all AEs in order to identify AEs leading to discontinuation.

In general, the items that are counted are:

- Disposition table: A subject who has, on the termination form, the reason for early termination “Serious Adverse Event” or “Other adverse event” is checked.

- Safety overview table: A subject who has either the reason for early termination “Serious Adverse Event” or “Other adverse event” checked or lists an AE on an AE page (solicited, unsolicited, or SAE) that has “Reaction Leading to Termination” or “Event Leading to Termination” or “Serious Adverse Event Leading to Termination” checked on the termination form, that is at least Grade 1 and is within the time period indicated
- System organ class/preferred term (SOC/PT) table: An event (solicited, unsolicited, or SAE) that has “Reaction Leading to Termination” or “Event Leading to Termination” or “Serious Adverse Event Leading to Termination” checked that is at least Grade 1 and is within the time period indicated

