4.3.2.2 Safety Endpoints

The observational endpoints for the evaluation of safety are:

- Occurrence, nature (Medical Dictionary for Regulatory Activities [MedDRA] preferred term), duration, intensity, and relationship to vaccination of any unsolicited systemic AEs reported in the 30 minutes after vaccination.
- Occurrence, time of onset, number of days of occurrence, intensity, action taken, and whether the reaction led to early termination from the study, of solicited (prelisted in the subject's diary card and electronic case report form [CRF]) injection site reactions occurring up to 7 days after vaccination.
- Occurrence, time of onset, number of days of occurrence, intensity, action taken, and whether the reaction led to early termination from the study, of solicited (prelisted in the subject's diary card and CRF) systemic reactions occurring up to 7 days after vaccination.
- Occurrence, nature (MedDRA preferred term), time of onset, duration, intensity, action taken, relationship to vaccination (for systemic AEs only), and whether the event led to early termination from the study, of unsolicited AEs up to Visit 2 after vaccination.
- Occurrence, nature (MedDRA preferred term), time of onset, duration, seriousness criteria, relationship to vaccination, outcome, and whether the SAE led to early termination from the study, of SAEs ██████████ throughout the trial.
- Occurrence, nature (MedDRA preferred term), time of onset, duration, seriousness, relationship to vaccination, and outcome for MAAEs from Visit 2 to the 6-month follow-up contact. MAAEs will be collected as unsolicited AEs up to Visit 2.

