4.4.1.2 Unsolicited Non-serious AEs

4.4.1.2.1 Presence

An observation will be considered an event if it has at least a verbatim term and is not a Grade 0 intensity event. Grade 0 events should be included in the listing “Unsolicited non-serious AEs not included in the safety analysis.”

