5.1.3.2.2 Safety

Safety results in [Section 4.3.2.2](#) will be described for subjects in all study groups. The main parameters for the safety endpoints will be described by 95% CIs (Clopper-Pearson method) (6). Analyses will contain at least the descriptions listed in [Table 5.2](#):

Table 5.2: Statistical analyses for safety observational objective

Safety Events	Time and Group	Description
Immediate unsolicited systemic AE	Within 30 minutes after injection for all subjects in Groups 1 and 2 at D0	Percentage of subjects that have the event, MedDRA terms, intensity, relationship to vaccine, study discontinuation
Solicited injection site reactions	Up to 7 days after D0 for all subjects in Groups 1 and 2	Percentage of subjects that have the event, onset, duration, intensity, action taken, study discontinuation, temperature collection routes
Solicited systemic reactions	Up to 7 days after D0 for all subjects in Groups 1 and 2	
Unsolicited AE	Up to 30 days after D0 for all subjects in Groups 1 and 2	Percentage of subjects that have the event, MedDRA terms, onset, duration, intensity, relationship, action taken, study discontinuation

^a rSBA vaccine seroresponse is defined as a post-vaccination titer $\geq 1:32$ for subjects with pre-vaccination rSBA titer $< 1:8$, or a post-vaccination titer ≥ 4 times the pre-vaccination titer for subjects with pre-vaccination rSBA titer $\geq 1:8$.

SAE [REDACTED]	Up to 6-month follow-up after D0 for all subjects in Groups 1 and 2	Percentage of subjects that have the event, MedDRA terms, onset, duration, relationship, seriousness criteria, outcome, study discontinuation
MAAE	Between Visit 1 and Visit 2 for all subjects in Groups 1 and 2 (as unsolicited AE) From Visit 2 to 6-month follow-up for all subjects in Groups 1 and 2	Percentage of subjects that have the event, MedDRA terms, onset, duration, intensity, relationship, action taken, study discontinuation

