5.3.1.4 Intensity

For solicited reactions, missing intensities will be handled as described in [Section 4.4.1.1.1](#). For unsolicited non-serious AEs, missing intensities will remain missing and will not be imputed.

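### The Grade 1 condition in SAP 4.4.1.5.5 literally leaves ungraded unsolicited AEs, and any SAE without a recorded grade, out of the SOC/PT table of AEs leading to discontinuation

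*SAP*

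**What the plan says.** SAP 4.4.1.5.5 starts from the statement that "A flag is available in the clinical database for all AEs in order to identify AEs leading to discontinuation". It then gives counting rules for three tables:

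- **Disposition table:** counts a subject by the reason ticked on the termination form. No grade is involved.
- **Safety overview table:** counts a subject either by that termination-form reason or by an AE-page event flagged as leading to termination. The flagged event must be at least Grade 1 and in period.
- **SOC/PT table:** counts events, not subjects. Its scope is "An event (solicited, unsolicited, or SAE) that has" a termination flag "checked that is at least Grade 1 and is within the time period indicated". There is no termination-form route.

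Four other places in the SAP bear on the grade condition:

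- 4.4.1.2.1 counts an unsolicited non-serious AE if "it has at least a verbatim term and is not a Grade 0 intensity event".
- 4.4.1.2.2 makes Missing an intensity class separate from None and Grades 1 to 3, and 5.3.1.4 adds: "For unsolicited non-serious AEs, missing intensities will remain missing and will not be imputed".
- For SAEs, the endpoint in 4.3.2.2 lists "time of onset, duration, seriousness criteria, relationship to vaccination, outcome, and whether the SAE led to early termination from the study", and the SAE row of Table 5.2 lists "Percentage of subjects that have the event, MedDRA terms, onset, duration, relationship, seriousness criteria, outcome, study discontinuation". Neither mentions intensity. The derivations in 4.4.1.3 cover last vaccination, onset and duration only.
- For solicited reactions, 4.4.1.1.3 sets presence at Grades 1 to 3 and treats a missing maximum intensity as missing presence.

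**The concern.** The SAP applies two inclusion rules to the same record. In the general AE tables an unsolicited non-serious AE is left out only if it is Grade 0. In the discontinuation table it is left out unless it has a grade of 1 or more. A record with no grade passes the first rule and fails the second.

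The same condition is applied to SAEs, for which the SAP supplies no grade and no rule for a missing one. A programmer who codes 4.4.1.5.5 as written would drop any SAE record whose grade is blank, although the rule names SAEs as countable.

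What is at stake is agreement between safety tables. A child withdrawn because of an ungraded event could be counted in the disposition table and the overview while no matching event appears in the SOC/PT discontinuation table. Events that lead to withdrawal are few and are read one by one, so a single unexplained gap is noticeable.

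**Working it through.** The SAP gives no discontinuation figure to reproduce. The check applies the wording of 4.4.1.5.5 to each kind of flagged, in-period event and compares the result with the rule that governs that event type elsewhere.

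| Flagged, in-period event | Rule elsewhere in the SAP | SOC/PT table under 4.4.1.5.5 | Consistent? |
|---|---|---|---|
| Solicited reaction, Grade 1 to 3 | Present (4.4.1.1.3) | Counted | Yes |
| Solicited reaction, maximum intensity missing | Missing presence, not analysed (4.4.1.1.3) | Not counted | Yes |
| Unsolicited non-serious AE, Grade 1 to 3 | Event (4.4.1.2.1) | Counted | Yes |
| Unsolicited non-serious AE, Grade 0 | Not an event (4.4.1.2.1) | Not counted | Yes |
| Unsolicited non-serious AE, grade missing | Event (4.4.1.2.1); grade stays missing (5.3.1.4) | Not counted | **No** |
| SAE with a recorded grade of 1 or more | No grade condition in 4.4.1.3 | Counted | Yes |
| SAE with no recorded grade | No grade condition in 4.4.1.3 | Not counted, although SAEs are named in scope | **No** |

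**Effect across tables.** Take a subject whose only flagged event falls in one of the two inconsistent rows.

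- Disposition: counted if the termination-form reason is an SAE or another AE.
- Overview: counted by the same termination-form reason; not counted by the AE-page route. This reads the grade condition as attached to the AE-page route only, which is the natural parsing of the sentence.
- SOC/PT: not counted by any route.

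**Other missing data.** The SAP treats other missing items in the opposite direction. Missing causality is taken as related (5.3.1.2), and events with missing onset stay in the analysis (4.4.1.2.4 and 4.4.1.3.2).

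**Size.** Let k be the number of flagged events in an arm, and suppose one is ungraded. The share of that arm's SOC/PT count that is lost is 1/k. The SAP gives no k, so k = 1 to 5 is an assumption:

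- k = 1: 1/1 = 100%
- k = 2: 1/2 = 50%
- k = 3: 1/3 = 33%
- k = 4: 1/4 = 25%
- k = 5: 1/5 = 20%

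At k = 0 nothing can be lost and the share is undefined. Against the planned 500 subjects per group, one subject is 1/500 = 0.2 percentage points.

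**The case against.** **SAE grades may be collected.** The endpoint list and Table 5.2 describe what is reported, not what is recorded. The SAE assessment section (4.3.2.3.4) is in the table of contents, but its text is not in the public copy. The SAP also shows that absence from an endpoint list proves little: the MAAE endpoint in 4.3.2.2 omits intensity, yet the MAAE row of Table 5.2, like the unsolicited AE row, reads "Percentage of subjects that have the event, MedDRA terms, onset, duration, intensity, relationship, action taken, study discontinuation". This objection stands. A reader might infer that SAEs as a class fall out of the table, but the document supports this only for an SAE that has no recorded grade.

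**The intent is clear.** The rule names SAEs and is introduced as a general convention. A reading that empties one of its three named categories is unlikely to be meant; the probable purpose is to screen out Grade 0 records. That is fair as to intent, and the SAP should not be read as wishing to omit SAEs. It does not change what the words do when programmed.

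**The event can be seen elsewhere.** A reader might infer that the SOC/PT table is the only place that names the event behind a withdrawal. It is not. The SAE and unsolicited AE rows of Table 5.2 provide for MedDRA terms and study discontinuation without a grade condition, so the event may surface there.

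**The tables differ by design.** One uses the form, one uses the form or a flag, and one uses the flag alone, so some disagreement is possible under any grade wording. That is true, but the grade condition adds a further difference that serves no stated purpose.

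**The condition is right for solicited reactions.** It matches 4.4.1.1.3. This also stands, so removing it for every event type would create a new inconsistency.

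**Conclusion.** The point holds in a limited form. For unsolicited non-serious AEs with missing intensity, 4.4.1.5.5 conflicts with 4.4.1.2.1 and 5.3.1.4 on the face of the text, whatever the CRF collects for SAEs. For SAEs the loss is conditional: it affects only those without a recorded grade, and the public copy does not show how many, if any, there could be.

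Few events are likely to be affected. The loss of 20% to 100% of an arm's SOC/PT count rests on two assumptions: 1 to 5 flagged events in the arm, and exactly one of them ungraded. Disagreement with the disposition and overview tables also requires that the termination-form reason was checked.

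Safety is descriptive, with no hypothesis attached, and the primary non-inferiority conclusion is untouched. This is a minor correction, but it concerns a stated counting rule that omits events it says it covers, so it is more than missing detail.

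**What to change.** In both the safety overview and SOC/PT bullets of 4.4.1.5.5, replace the single grade condition with one for each event type:

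- **Solicited reactions:** keep Grade 1 or higher, consistent with 4.4.1.1.3.
- **Unsolicited non-serious AEs:** require that the event is not Grade 0, and state that an event with missing intensity is counted, consistent with 4.4.1.2.1.
- **SAEs:** count every flagged, in-period SAE regardless of grade.

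The cost is a short wording change and one programming condition per event type. Counts for events with a recorded grade of 1 or more do not change, and no endpoint, test or data collection is affected.

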4.4.2 Immunogenicity

4.4.2.1 Computed Values for Analysis

In order to appropriately manage extreme values ($< \text{LLOQ}$ and $\geq \text{ULOQ}$) for analysis purposes, the following computational rule is applied to the values provided in the clinical database for each blood sample (BL) drawn:

- If a value is $< \text{LLOQ}$, then use the computed value $\text{LLOQ}/2$
- If a value is between $\geq \text{LLOQ}$ and $< \text{ULOQ}$, then use the value
- If a value is $\geq \text{ULOQ}$, then use the computed value ULOQ

4.4.2.2 Seroprotection

Not applicable

4.4.2.3 Fold-rise

The derived endpoint fold-rise is driven by both baseline and post-baseline computed values and is computed as follows. Generally, for extreme values, this algorithm minimizes the numerator and maximizes the denominator.

- If the baseline computed value is $< \text{LLOQ}$ and the post-baseline computed value is $< \text{LLOQ}$, then the fold-rise is 1
- If the baseline computed value is $\geq \text{LLOQ}$ and the post-baseline computed value is $\geq \text{LLOQ}$, then the fold-rise is $\text{post-baseline computed value} / \text{baseline computed value}$
- If the baseline computed value is $\geq \text{LLOQ}$ and the post-baseline computed value is $< \text{LLOQ}$, then the fold-rise is $(\text{LLOQ}/2) / \text{baseline computed value}$
- If the baseline computed value is $< \text{LLOQ}$ and the post-baseline computed value is $\geq \text{LLOQ}$, then the fold-rise is $\text{post-baseline computed value} / \text{LLOQ}$

Note: If baseline or post-baseline is missing, then fold-rise is missing.

4.4.2.4 A, C, Y, W Seroresponse

hSBA vaccine seroresponse for serogroups A, C, Y, and W is defined as:

- For a subject with a pre-vaccination titer $< 1:8$, the post-vaccination titer must be $\geq 1:16$.
- For a subject with a pre-vaccination titer $\geq 1:8$, the post-vaccination titer must be at least 4-fold greater than the pre-vaccination titer.

rSBA vaccine seroresponse for serogroups A, C, Y, and W is defined as:

- Post-vaccination rSBA titers $\geq 1:32$, if pre-vaccination rSBA titers $< 1:8$ or
- At least a 4-fold increase in rSBA titers from pre- to post-vaccination, if pre-vaccination rSBA titers $\geq 1:8$.

4.4.3 Efficacy

Not applicable

4.4.4 Derived Other Variables

4.4.4.1 Age for Demographics

Age in years: $(\text{Date of vaccination} - \text{Date of birth} + 1) / 365.25$

4.4.4.2 Subject Duration

The duration of a subject in the study is computed as follows: Maximum (date of last visit, date of term form) – (date of Visit 1) +1.

The duration of a subject in the study including follow-up is computed as follows: Maximum (date of last visit, date of term form, last date of follow-up contact) – (date of Visit 1) +1.

4.4.4.3 Duration of the Study

The duration of the study (until last visit) is computed as follows: Maximum of all subjects (date of last visit, date of termination form) – minimum for all subjects (date of Visit 1) +1.

The duration of the study (including follow-up) is computed as follows: Maximum of all subjects (date of last visit, date of termination form, date of last follow-up contact) – minimum for all subjects (date of visit V01) +1

5 Statistical Methods and Determination of Sample Size

The statistical analyses will be performed under the responsibility of the Sponsor's Biostatistics platform using SAS[®] Version 9.4 software or later. The results of the statistical analysis will be available in the final clinical study report (CSR).

For descriptive purposes, the following statistics in Table 5.1 will be presented. The confidence interval (CI) for the single proportion will be calculated using the exact binomial method (Clopper-Pearson method, quoted by Newcombe (6)). For immunogenicity results, assuming that Log₁₀ transformation of the titers / data follows a normal distribution, at first, the mean and the 95% CI will be calculated on Log₁₀ (titers / data) using the usual calculation for normal distribution (using Student's t distribution with n-1 degree of freedom), then antilog transformations will be applied to the results of calculations, in order to provide geometric means (GMs) and their 95% CI.

Table 5.1: Descriptive statistics produced

Baseline characteristics and follow-up description	Categorical data	Number of subjects. Percentage of subjects.
	Continuous data	Mean, standard deviation, quartiles, minimum, and maximum.
Clinical safety results	Categorical data	Solicited: Number and percentage (95% CIs) of subjects. Unsolicited: Number and percentage (95% CIs) of subjects, and number of events.
Immunogenicity results	Categorical data (seroresponse, vaccine response, seroconversion, cutoff)	Number and percentage (95% CIs) of subjects.
	Continuous data (titer / data)	Log ₁₀ : Mean and standard deviation. Anti-Log ₁₀ (work on Log ₁₀ distribution, and anti-Log ₁₀ applied): Geometric mean (GM), 95% CI of the GM Graphical representation by Reverse Cumulative Distribution Curve (RCDC).

5.1 Statistical Methods

5.1.1 Hypotheses and Statistical Methods for Primary Objective

5.1.1.1 Hypotheses

Thirty days^a after the administration of MenACYW conjugate vaccine or MENVEO[®], the percentages of subjects who achieve an hSBA vaccine seroresponse^b for meningococcal

^a D30 (+14 days)

^b The hSBA vaccine seroresponse for serogroups A, C, Y, and W is defined as:

serogroups A, C, Y, and W in Group 1 are non-inferior to the corresponding percentages in Group 2.

Null hypothesis (H_0): $p_{(G1)} - p_{(G2)} \leq -10\%$

Alternative hypothesis (H_1): $p_{(G1)} - p_{(G2)} > -10\%$

where $p_{(G1)}$ and $p_{(G2)}$ are the percentages of subjects who achieve an hSBA vaccine seroresponse in Group 1 and Group 2, respectively.

5.1.1.2 Statistical Methods

Each of the serogroups A, C, Y, and W will be tested separately. If the lower limit of the 2-sided 95% confidence interval (CI) of the difference between the 2 percentages is $> -10\%$, the inferiority assumption will be rejected. For the 4 non-inferiority hypotheses using the seroresponse rates, the CI of the difference in percentages ($p_1 - p_2$) will be computed using the Wilson Score method without continuity correction (7).

Let $\hat{\theta} = p_1 - p_2$, then $L = \hat{\theta} - \delta$ and $U = \hat{\theta} + \varepsilon$ are respectively the lower and the upper limits of the CI, where:

$$\delta = Z_{0.025} \sqrt{\left\{ \frac{l_1(1-l_1)}{n_1} + \frac{u_2(1-u_2)}{n_2} \right\}}$$

$$\varepsilon = Z_{0.025} \sqrt{\left\{ \frac{l_2(1-l_2)}{n_2} + \frac{u_1(1-u_1)}{n_1} \right\}}$$

l_1 and u_1 are calculated from the CI of the single proportion in Group 1 given by:

$$\frac{(2n_1p_1 + Z_{0.025}^2 \pm Z_{0.025} \sqrt{(Z_{0.025}^2 + 4n_1p_1(1-p_1))})}{2(n_1 + Z_{0.025}^2)}$$

l_2 and u_2 are calculated from the CI of the single proportion in Group 2 given by:

$$\frac{(2n_2p_2 + Z_{0.025}^2 \pm Z_{0.025} \sqrt{(Z_{0.025}^2 + 4n_2p_2(1-p_2))})}{2(n_2 + Z_{0.025}^2)}$$

where $Z_{0.025}$ is the upper 97.5th percentile of the standard normal distribution.

The overall non-inferiority of this objective will be demonstrated if all 4 individual null hypotheses are rejected.

-
- For a subject with a pre-vaccination titer $< 1:8$, the post-vaccination titer must be $\geq 1:16$.
 - For a subject with a pre-vaccination titer $\geq 1:8$, the post-vaccination titer must be at least 4-fold greater than the pre-vaccination titer.

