3.1 Trial Design

This is a Phase III, modified double-blind, randomized, parallel-group, active-controlled, multi-center trial to evaluate the immunogenicity and describe the safety of MenACYW conjugate vaccine compared to the MENVEO[®] in healthy children 2 to 9 years of age in the United States.

Healthy, meningococcal-vaccine naïve children aged 2 to 9 years will be randomized in a 1:1 ratio as follows:

- Group 1: MenACYW conjugate vaccine: N = 500
 - Group 1a: 250 children 2 to 5 years of age^a
 - Group 1b: 250 children 6 to 9 years of age^b
- Group 2: MENVEO[®]: N = 500
 - Group 2a: 250 children 2 to 5 years of age^a
 - Group 2b: 250 children 6 to 9 years of age^b

All subjects will provide blood samples for immunogenicity assessment at baseline (pre-vaccination) and at 30 to 44 days after vaccination.

Solicited adverse event (AE) information will be collected for 7 days after vaccination; unsolicited AE information will be collected from Visit 1 (Day [D] 0) to Visit 2 (D30 [+14 days]) and serious adverse event (SAE) information [REDACTED] will be collected throughout the study period from D0 through D180 (+14 days) after vaccination.

Medically-attended adverse events (MAAEs) will be collected throughout the study from Visit 1 through Visit 2 (as part of the collection of unsolicited AE information) and from Visit 2 through D180 (+14 days) (as MAAEs).

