5.1.2.2 Statistical Methods

5.1.2.2.1 For Secondary Objective 1

Thirty days^a after the administration of MenACYW conjugate vaccine or MENVEO[®], the hSBA geometric mean titer ratio (GMTR) between Group 1 and Group 2 will be calculated and 95% CI will be provided as follows.

Logarithm transformation of the individual titers will be calculated. Assuming that individual $\log_{10}(\text{titer})$ is normally distributed, the 95% CI for the difference in $\log_{10}(\text{GMT})$ between Group 1 and Group 2 will be in the form:

$$\bar{X}_1 - \bar{X}_2 \pm t(1 - \alpha/2, n_1 + n_2 - 2) \cdot S \sqrt{1/n_1 + 1/n_2}$$

where $\bar{X}_i = \log_{10}(\text{GMT})$ is the mean of $\log_{10}(\text{titer})$ of Group i ,

$S^2 = [(n_1 - 1) S_1^2 + (n_2 - 1) S_2^2] / (n_1 + n_2 - 2)$ is the pooled sample variance,

n_i and S_i^2 are the sample size and sample variance of Group i ,

$t(1 - \alpha/2, n_1 + n_2 - 2)$ is the 100(1- $\alpha/2$) percentile of the t -distribution with degrees of freedom $df = n_1 + n_2 - 2$.

The 95% CI for the hSBA GMTR between Group 1 and Group 2 will be formed by taking the antilogarithms of the lower and upper limits of the 95% CI for the difference in $\log(\text{GMT})$ between both vaccine groups.

5.1.2.2.2 For Secondary Objective 2

Thirty days^a after the administration of MenACYW conjugate vaccine or MENVEO[®] in children 2 to 5 years of age, and in children 6 to 9 years of age, respectively, the hSBA GMTR between Group 1a and Group 2a, and between Group 1b and Group 2b will be calculated and 95% CI will be provided, respectively, as described in Section 5.1.2.2.1.

5.1.2.2.3 For Secondary Objective 3

Thirty days after the administration of MenACYW conjugate vaccine or MENVEO[®] in children 2 to 5 years of age, and in children 6 to 9 years of age, respectively, the difference of hSBA vaccine

^a D30 (+14 days)

seroresponse^a rates between Group 1a and Group 2a, and between Group 1b and Group 2b will be calculated and 95% CI will be provided, respectively, as described in Section 5.1.1.2.

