5.2.4 Populations Used in Analyses

All immunogenicity analyses will be performed on the PPAS. Additional immunogenicity analyses will be performed for exploratory purposes on the FAS. In the FAS, subjects will be analyzed by the vaccine group to which they were randomized.

All safety analyses will be performed on the SafAS. Subjects will be analyzed according to the vaccine they actually received.

^a For which safety data are scheduled to be collected

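### The primary non-inferiority interval and the overall GMTR do not use the two age groups whose sizes the design fixes; stratifying by age would be a nearly free, optional gain in robustness

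*SAP*

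**What the plan says.** SAP 3.1 states that children "will be randomized in a 1:1 ratio as follows" and lists four cells: "Group 1a: 250 children 2 to 5 years of age", "Group 1b: 250 children 6 to 9 years of age", "Group 2a: 250 children 2 to 5 years of age" and "Group 2b: 250 children 6 to 9 years of age". It does not say that randomization is stratified by age; the fixed cell sizes only imply it.

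SAP 5.1.1.2 tests each serogroup against a margin of -10 percentage points and requires all four to pass. The interval "will be computed using the Wilson Score method without continuity correction (7". Its inputs are the overall proportions p1 and p2 and the overall sizes n1 and n2.

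SAP 5.1.2.2.1 takes the overall GMTR from a two-sample t interval in which S² "is the pooled sample variance", again across both ages.

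On the analysis set, SAP 5.2.4 says "All immunogenicity analyses will be performed on the PPAS", with FAS analyses as exploratory. No age-stratified version of the primary interval is listed, either as the main analysis or as a sensitivity analysis. Age does appear elsewhere: secondary objectives 2 and 3 give GMTRs and seroresponse differences with 95% intervals within each age group, and 5.1.4 adds output by age group.

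**The concern.** Age group is the one baseline factor built into the size of the trial, and the confirmatory interval does not use it. Two things could follow.

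- **Precision.** If seroresponse differs by age, the crude interval counts the between-age variation as error, although equal cells have already balanced it between arms.
- **Age mix.** The PPAS is formed after randomization. Under 5.2.3, children drop out of it for missing or out-of-window samples, invalid results or prohibited medication. If this happens unevenly by arm and age, the crude difference mixes age with vaccine.

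The second matters more, because the pass or fail decision for each serogroup rests on this interval alone. The within-age results are descriptive and cannot change that decision.

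**Working it through.** **Inputs.** From the SAP: 250 per cell (3.1), margin -10 points, two-sided 95% interval (5.1.1.2). The sample-size section (5.5) is redacted, so there is no stated power or rate to reproduce. Assumed: seroresponse rates, age gaps, evaluable numbers (225 per cell, 450 per arm), the PPAS age mix and a within-age SD of 0.6 log10.

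**1. Precision, equal cells.** Let the age-specific rates be pa and pb, with mean p and m children per cell.
- Crude SE = sqrt(2p(1-p)/(2m)).
- Stratified SE = sqrt(2[0.25·pa(1-pa)/m + 0.25·pb(1-pb)/m]).
- Ratio = sqrt(1 - (gap²/4)/(p(1-p))).

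With m = 250 and p = 50%, the crude half-width is 1.96 × 0.0316 = 6.20 points.

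| Age gap (points) | Stratified half-width (points) | Ratio |
|---|---|---|
| 0 | 6.20 | 1.000 |
| 10 | 6.17 | 0.995 |
| 20 | 6.07 | 0.980 |
| 30 | 5.91 | 0.954 |
| 40 | 5.68 | 0.917 |

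At p = 60% the ratios for gaps of 20 and 40 points are 0.979 and 0.913.

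**2. Error and power, equal cells.** Simulation with mean rate 60% and 225 per cell:
- 20-point gap: crude one-sided error 2.3%; power per serogroup at no true difference 87.4% crude, 87.8% to 88.5% stratified.
- 40-point gap: crude error 1.6%; power 89.1% crude, 91.9% to 92.2% stratified.

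The lower stratified figure is a Wald form, the higher one a Newcombe form combined stratum by stratum.

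**3. Unequal age mix.** Bias of the crude difference = difference in age share × age gap. For 47% v 50% aged 2 to 5 and a 20-point gap, this is 0.03 × 20 = 0.6 points. It favours the new vaccine if older children respond better and Group 1 has fewer young children.

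A normal approximation shows what this does to the error. Take control rates 50%/70% and a true difference of -10 points at both ages, so Group 1 is 40%/60%.
- SE used by the crude interval: sqrt((0.25 + 0.24)/450) = 0.0330.
- Actual SD with age shares fixed: sqrt((0.24 + 0.23)/450) = 0.0323.
- Balanced: threshold 1.96 × 0.0330/0.0323 = 2.00, error about 2.3%.
- Bias +0.6 points: (0.0647 - 0.006)/0.0323 = 1.82, error about 3.5%.
- Bias -0.6 points: (0.0647 + 0.006)/0.0323 = 2.19, error about 1.4%.

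Simulation with the actual 5.1.1.2 formula gives 3.5% to 3.6% and, reversed, 1.5%. Stratified intervals give about 2.4% to 2.7%.

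**4. Which stratified Newcombe interval.** Putting Mantel-Haenszel-weighted Wilson limits into the existing 5.1.1.2 formula gives no gain: power 87.4% v 87.4% at a 20-point gap and 89.1% v 89.1% at 40 points. Combining the deviations stratum by stratum does recover the gain, so the construction must be named.

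**5. Overall GMTR.** Pooled SD = sqrt(0.36 + d²/4) for an age difference d in mean log10 titre. For d = 0.1, 0.2, 0.3 and 0.5, an age term narrows the interval on the log scale by 0.3%, 1.4%, 3% and 8%.

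**The case against.** The strongest reply is that nothing in the plan is wrong. The hypotheses in 5.1.1.1 concern the overall percentages, and 5.1.1.2 estimates exactly that difference with a recognised interval. With equal cells the test is valid, and any departure from 2.5% is on the safe side; stratifying then moves the false-claim rate up towards nominal. The precision gain is invisible at a 10-point gap and small at 20. Bias needs an age gap together with attrition that differs by arm and age, and 0.6 points is small against a 10-point margin. Within-age differences are already planned, so a reader could see an imbalance and re-weight.

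Most of this stands. Two parts do not fully answer the point. Re-weighting after unblinding would be post hoc, and the descriptive within-age results do not enter the decision. And a 0.6-point shift, although small against the margin, is enough to move the one-sided error by about one percentage point.

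A reader might infer that the plan disregards age, that precision is certainly lost, or that the primary test has an inflated error rate. The SAP supports none of these: age-specific analyses are planned, loss of precision depends on an age gap that the SAP does not show, and inflation depends on an imbalance that equal planned cells make less likely.

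**Conclusion.** The omission is real, but it concerns robustness and efficiency, not validity. With balanced cells the crude interval is valid and at most conservative. Stratifying saves nothing without an age gap, about 2% of interval width at 20 points and about 8% at 40.

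The better reason to stratify is protection against an uneven age mix in the PPAS: at an assumed 47% v 50% and a 20-point gap, crude error is about 3.6% in one direction and 1.5% in the other, against about 2.5% stratified. A larger assumed imbalance (200 younger and 240 older v 230 and 235) gives 4.1% at a 20-point gap, or 1.3% reversed, at a mean rate of 50%.

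Every size here rests on assumed rates, gaps and attrition. That all four serogroups must pass would multiply a loss only if several serogroups had such a gap, and none is shown. The GMTR part is weaker still, because 5.1.2.1 tests no hypothesis there. In weight this is optional.

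**What to change.** - **5.1.1.2.** Estimate each serogroup difference as Σ w_i(p1i - p2i) over the two age groups, with Mantel-Haenszel weights w_i proportional to n1i·n2i/(n1i + n2i) and summing to 1. Lower 95% limit = weighted difference - sqrt(Σ w_i²[(p1i - l1i)² + (u2i - p2i)²]); upper limit = weighted difference + sqrt(Σ w_i²[(u1i - p1i)² + (p2i - l2i)²]), where l and u are the within-stratum Wilson limits. State that pooled stratified Wilson limits are not to be put into the present formula. Judge against the same -10% margin and keep the crude interval as supportive.
- **Minimum version.** Leave the crude interval as primary and pre-specify the stratified one as a sensitivity analysis.
- **5.1.2.2.1.** Take the GMTR from a linear model of log10 titre on vaccine and age group. This is descriptive only.

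The cost is SAP wording and a small programming change before unblinding, with no new data or children. When the age shares match between arms, the weighted difference equals the crude one.
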